10. STUDY ASSESSMENTS AND PROCEDURES

EFFICACY ASSESSMENTS

The main drug efficacy measure for this study is neurodegeneration (secondary objective). We will derive annual brain atrophy rates by comparing volumetric MRI (vMRI) values for the hippocampal, cortical, and global thickness. All 105 study participants will undergo vMRI at Baseline (Week 0) and after 6 months, 12 months, and 18 months.

To demonstrate clinical utility, it is necessary to show that a possible treatment for AD can slow down or reverse cognitive decline. Thus, our tertiary objective (and secondary efficacy endpoint) will assess cognition in all study subjects. For this, we will employ the recently created, high-sensitivity

Alzheimer’s Disease Composite Score (ADCOMS), which is recommended for mild AD in clinical trials of 12 months’ duration or longer⁴¹. Briefly, ADCOMS consists of 4 Alzheimer’s Disease Assessment Scale-cognitive subscale items (ADAS-Cog13), 2 Mini-Mental State Examination items (MMSE), and all 6 Clinical Dementia Rating-Sum of Boxes items (CDR-SOB)⁴¹. ADCOMS will be administered at specified time points throughout the study (refer to study table 1). Furthermore, to assess conversion to AD or reversion to normality, we will repeat the cognitive measurements at 18 months (Week 78). This time was selected because the calculated mean time for conversion from aMCI to AD in the literature ranges from 12-20 months¹⁶. Thus, measuring cognitive performance 18 months after the start of the trial should provide us with a good assessment of whether Sisonimod is effective at slowing down cognitive decline. A positive effect of Sisonimod on cognitive outcome measures would translate into increased ADCOMS scores at the end of dosing vs. Baseline and/or a slower decline than in placebo-treated subjects at month 18.

Additional objectives (exploratory efficacy endpoints) are (i) an additional assessment of cognitive performance via the ADCS-ADL test administered every 6 months; and (ii) the measurement of biomarkers in the CSF, blood, and saliva, to explore the possibility of using biofluid markers as proxy of drug efficacy. For example, since Sisonimod is an immunomodulator that prevents the egression of T lymphocytes from peripheral lymphoid organs, we should observe a decrease in circulating T lymphocytes and inflammatory markers in the blood samples we collect during the entire course of this clinical trial.

All procedures are carried out by trained medical staff and scientists used to conduct clinical trials at the study site. Labs (CBC with differential and CMP) analyses are performed by a contracted medical laboratory, therefore follow GCP standards.

+ Neurodegeneration Measures

- Volumetric MRI

MR imaging will be conducted on a 3T MRI scanner located in Phoenix, AZ. Sequences will include a high resolution 3D T1-weighted magnetization prepared rapid acquisition gradient echo (MPRAGE), a T2-weighted image, a 3D FLAIR image, and a high-resolution T1 image of the hippocampus. Each individual scan will be less than 7 minutes in length and will match protocols developed by the Alzheimer’s disease neuroimaging initiative (ADNI). Other imaging may include advanced diffusion and perfusion . Each of these scans will be less than 10 minutes in duration, and the overall scan time will be less than 1 hour.

40 min sequence (estimated 38 min 26 s)

Sequence	Approx. run time in minutes
T1-weighted MPRAGE	6:11
T2-weighted image	6:42
T2-weighted FLAIR	6:10
High Res Hippo	5:36
Diffusion MRI	8:05
Perfusion MRI	5:32

+ Cognitive Measures

- Alzheimer’s Disease Assessment Scale - Cognitive

Alzheimer’s Disease Assessment Scale - Cognitive (ADAS-cog)³⁶ is a psychometric instrument that evaluates memory, attention, reasoning, language, orientation, and praxis. A higher score indicates more impairment; the range is 0 to 89. We will use the ADAS-cog13 as it is the currently accepted scale used by clinicians to detect changes in mildly demented subjects.

- Clinical Dementia Rating-Sum of Boxes

The Clinical Dementia Rating - Sum of Boxes (CDR-SOB) test³⁴ is a commonly used instrument in MCI studies. The CDR-SOB describes five degrees of impairment in performance on each of 6 categories of cognitive functioning including memory, orientation, judgment and problem solving, community affairs, home and hobbies, and personal care. The ratings of degree of impairment obtained on each of the 6 categories of function are synthesized into one global rating of dementia (ranging from 0 to 3), with more refined measure of change available by use of the Sum of Boxes. The CDR-rater will be a trained clinician. Ideally the same CDR rater will be used throughout the course of the trial when possible.

- Mini Mental State Examination

The Mini Mental State Examination (MMSE) is a screening instrument frequently used in Alzheimer's disease drug studies.¹¹ It evaluates orientation, memory, attention, concentration, naming, repetition, comprehension, and the ability to create a sentence and copy two intersecting pentagons. Scores range from 0 to 30, with 30 being the score assigned to cognitively normal individuals. The range for mild AD is 21-26.

- Alzheimer's Disease Cooperative Study - Activities of Daily Living

In the Alzheimer's Disease Cooperative Study - Activities of Daily Living (ADCS-ADL) test, study partners are queried via a structured interview format as to whether subjects attempted each item in the inventory during the preceding four weeks, as well as their level of performance¹⁴. This will provide a reliable estimate of daily functioning. ADCS-ADL is not part of the ADCOMS computation. It will be administered every 6 months, as done routinely for our clinical trials.

- ADCOMS

The AD Composite Score (ADCOMS) consists of 4 ADAS-Cog items, 2 MMSE items, and all 6 CDR-SOB items [PMID: 27010616]. The ADCOMS was derived with the intention of using it as a primary outcome measure for registration trials of disease-modifying treatments in persons with predementia and early AD-related dementia. The ADCOMS has demonstrated improved sensitivity over each individual scale comprised in the composite and requires smaller sample sizes to detect longitudinal cognitive changes. Retrospective analyses have shown that ADCOMS is superior to other measures in detecting and measuring early cognitive decline and disease progression among patients with early stages of AD, i.e. mild cognitive impairment and mild AD [PMID: 35099758]. Thus, the ADCOMS appears as the most promising cognitive composite score for the present study.

+ Biomarkers

- Exploratory Blood Biomarkers

Because CSF collection is not possible at each site visit, we explore the possibility of using blood inflammatory markers as surrogate markers of Sisonimod efficacy. For this, we will collect whole blood (cubital vein); maximum 45 mL in tubes containing ethylenediaminetetraacetic acid (EDTA). After differential centrifugations, we will measure plasma C-reactive protein, TNF- α , IL-1 β , IL-6, IL-8, and IL-10 by multiplex ELISA (Meso Scale Discovery 54 Plex for human inflammatory markers).

+ Exploratory Saliva Biomarkers (Optional Sub-Study)

In recent years, saliva amyloid beta levels have shown good performance at discriminating AD vs. cognitively normal subjects. For example, the lead PI has published a proof-of-concept study on a few subjects that showed increased levels of saliva A β 42 in AD patients compared to age- and gender-matched cognitively normal controls³⁷. Thus, in an exploratory effort we will offer to our study subjects the option to donate saliva at specified points in the study (see table 1) to determine whether A β 40 and A β 42 levels in saliva are affected by long-term treatment with Sisonimod.

+ Exploratory CSF Biomarkers (Optional Sub-Study)

As there is currently no effective treatment for AD, it is unclear how the levels of CSF biomarkers associated with the disease (e.g., amyloid beta 40 and 42, total tau, phospho-tau; all measured on the

Meso Scale Discovery multiplex ELISA platform) may change after a positive outcome induced by a disease-modifying therapy. Therefore, in the present study we will analyze these biomarkers in the CSF. In addition, because Siponimod is an immunomodulator, we will assess CSF inflammatory markers as a possible proxy for drug efficacy. LPs will be carried out at Baseline (Week 0) and end of dosing (Week 52). For this, we will measure the levels of CSF C-reactive protein, TNF- α , IL-1 β , IL-6, IL-8, and IL-10 by multiplex ELISA (Meso Scale Discovery 54 Plex for human inflammatory markers).

+ Appropriateness of Measurements

The efficacy measures assessed in this study are appropriate for the evaluation of AD therapies. All cognitive tests we use are validated for the assessment of AD status and progression. The imaging and plasma biomarkers we are investigating are the most likely to demonstrate an alteration of AD neuropathologies and inflammation.

SAFETY AND OTHER ASSESSMENTS

Safety will be evaluated by assessing AEs, clinical laboratory data, vital signs, and concomitant medications. The investigator is responsible for monitoring the safety of study subjects and providing appropriate medical care during the study. Any significant safety issues should be discussed with the Medical Monitor and DSMB in a timely manner.

- Protection Against Privacy Risk

Every effort will be made to ensure the privacy of participant PHI and confidentiality by utilizing secure EMR and databases. Paper copies are filed by number in accordance with professional standards of privileged information. All documentation and case reports forms are compliant with HIPAA regulations. Confidentiality is safeguarded by strict adherence to these standards.

- Safety Monitoring

An independent Data Safety Monitoring Board (DSMB) comprised of three members not associated with the study will be secured prior to starting the study. This group of experts advises NIH and the Sponsor/Investigator. During the trial, the DSMB will review cumulative study data to evaluate safety, study conduct, and scientific validity and integrity of the trial. ...

A Medical Monitor has been secured to provide medical expertise to the study team including answering investigator questions about the protocol, patient eligibility and the medical management of subject AE/SAE assessment/treatment, and/ or medical emergencies.

There will also be a Study Monitor who is responsible for monitoring the conduct of the clinical trial on a regular basis as per GCP and ICH guidelines. He/she will inspect the case report forms at regular intervals throughout the study to verify adherence to the protocol; completeness and accuracy of the data; and adherence to local regulations on the conduct of clinical research. The investigators agree to cooperate with the study monitor to ensure that any problems detected during these monitoring visits are resolved.

The study monitor will inspect site facilities (e.g., pharmacy, drug storage areas, laboratories) and review study-related records to evaluate the trial conduct and compliance with the protocol, GCP, and applicable regulatory requirements. Results of locally administered tests such as EKG tracings and local clinical laboratory reports will be retained as source documents. At the monitoring visits, the progress of the study will be discussed with the Investigator and/or the Study Coordinator and the informed consent forms and CRFs will be checked for completeness and accuracy. Subjects' source documents should be available for review.

The investigators will immediately inform the Medical Monitor and the DSMB in case of moderate to severe adverse events, as well as when an individual subject is temporarily removed from dosing due to hematologic signs of toxicity (e.g. thrombocytopenia and/or neutropenia). All early

terminations will also be indicated to the DSMB in a timely manner. The IRB will be notified per Barrow Neurological Institute IRB Policy regarding Adverse Events Reporting.

- Complaint Handling

The investigator or his/her designee is responsible for handling the following aspects of the product complaint process in accordance with the instructions provided for this study:

- recording a complete description of the product complaint reported and any associated AEs using the study-specific complaint forms provided for this purpose.
- informing the medical monitor within 24-48 business hours of subject complaints.

- Safety Measures

+ Routine Clinical Laboratory Tests

Routine hematology, blood chemistry will be performed at screening and subsequent follow-up visits as described in the schedule of events.

+ Electrocardiograms

For each subject, 12-lead digital electrocardiograms (EKGs) will be collected according to the Schedule of Events. The EKG at screening will be a single EKG and will be interpreted by the principal investigator, or sub-investigator. Every effort will be made to obtain EKGs around the same time of day; however, if unable to schedule for the same time, EKGs will still be completed per protocol. Patients must be supine for approximately 5 to 10 minutes before EKG collection

. EKGs will be interpreted by the principal investigator, or sub-investigator, with every effort made to have EKG results reviewed as close to time of collection as possible. Ideally EKG result review will be completed while the subject is still at site, so that any clinically relevant findings are identified with subject present.

After enrollment, if a clinically significant increase in the QT/corrected QT (QTc>500) interval from baseline, or other clinically significant quantitative or qualitative change from baseline, is present, the investigator will assess the subject for symptoms (for example, palpitations, near syncope, syncope) and to determine if the subject can continue in the study. The investigator, or qualified designee, is responsible for determining if any change in patient management is needed and must document their review of the EKG printed at the time of evaluation along with the final overread EKG and any alert reports.

+ Physical Examination

A complete physical examination (with neurological exam) will be performed at the visits listed in the study protocol and schedule of events. An abbreviated physical examination, to include an ophthalmic examination and routine examination of the heart, lungs, abdomen, skin, and oral cavity, will also be performed. Sitting vital signs (blood pressure, heart rate, respiratory rate, and temperature), after each subject sits quietly for at least 5 minutes, and body weight will be assessed at the Screening Visit and at each subsequent visit.

+ Vital Signs

Body temperature (oral or tympanic) will be measured as specified in the Schedule of Activities and as clinically indicated.

Blood pressure and pulse rate (PR) will be measured as specified in the Schedule of Activities and as clinically indicated. Blood pressure and PR should be measured after at least 5 minutes of sitting.

+ Body Weight and Height

Body weight and height will be recorded as specified in the Schedule of Activities and as clinically indicated.

+ Neurological Examination

A directed neurological examination will be performed by the investigator at the time points specified in the protocol and schedule of events.

Any clinically significant change from baseline on follow-up physical/neurological examinations should be recorded as an AE and reported in the CRF. If additional ARIA-H, ARIA-E, are detected, an additional neurological exam may be performed by the investigator.

- Toxicity Assessment

During visits at the study site, we will collect blood samples and conduct blood counts and comprehensive metabolic panels to monitor hematologic and metabolic toxicities. All lab results will be reviewed by the primary investigator, or sub-investigators, to determine if any clinically significant findings are seen that could be attributed to Siponimod related toxicities.

- Procedure Used in Case of Toxicity

If toxicities are identified, we apply a special toxicity protocol. The hematologic or chemistry values indicative of severe AEs are those listed in exclusion criteria.

If toxicity, including cardiac SAEs, is suspected, or proven, to be linked to Siponimod, subjects will stop taking the study drug for 7 days, and undergo new blood tests after at least 7 days of washout. If test results continue showing toxicity, subjects will be withdrawn from the study and not replaced if this occurs after Visit 7.

If toxicity markers improve, subjects will resume dosing at the prior lower dose (i.e., toxic dose minus 0.25 mg) and remain on this regimen until the end of the study. In case of a second toxic event, dosing will again be stopped for 7 days, and blood tests conducted. If the test results continue showing toxicity, subjects will be withdrawn and not replaced if this occurs after Visit 7. If toxicity markers improve, subjects will resume dosing at the previous lower dose (i.e., toxic dose minus 0.25 mg) and remain at this lower dose until the end of the study.

In case of a third toxic event, subjects will be withdrawn and not replaced if this occurs after Visit 7. When study medication is withdrawn, study subjects will be recorded as “End Of Study Drug Visit” and undergo the corresponding assessments (Week 52 in Table 1). Then, the subjects will be asked to complete the corresponding washout period schedule of assessments: (Week 56 in Table 1) and 26 week “End of Study” (Week 78 in Table 1).

- Tolerability Assessment

Tolerability of Siponimod in study subjects will be derived from the frequency of AEs and study withdrawal motivated by subjects’ discomfort during the dosing period.

- Standard MRI (screening 1)

Patients who do not have an MRI scan within the past 12 months of Screening Visit Day 1 will be scheduled for an vMRI or CT during the screening period with results obtained before randomization is decided. (MRI is preferred).

>> Routine MRI Scan (default choice)

MR imaging will be conducted on a 3T MRI scanner located in Phoenix, AZ. Sequences will include a high-resolution 3D T1-weighted magnetization prepared rapid acquisition gradient echo (MPRAGE), a T2-weighted image, a 3D FLAIR image, and a high-resolution T1 image of the hippocampus. Each individual scan will be less than 7 minutes in length and will match protocols developed by the Alzheimer’s disease neuroimaging initiative (ADNI). Other imaging may include advanced diffusion, perfusion, spectroscopy, and functional MRI. Each of these scans will be less than 10 minutes in duration, and the overall scan time will be less than 1 hour. With the acquired T1 and T2 images, hippocampal, ventricular and whole brain volumes will be determined by automated segmentation using Freesurfer 6.0. Cortical thicknesses and subcortical volumes are also determined from this automated segmentation. With the high-resolution hippocampus T1 image, we are able to obtain the volumes of hippocampal subfields by using ASHS atlas. Voxelwise measures of regional gray matter volumes (corrected for the total intracranial volume) are determined using voxel-based morphometry in SPM8

and the longitudinal whole brain atrophy are estimated using iterative principal component analysis. Furthermore, voxel-wise whole brain morphological changes are determined using deformation-based morphometry with high resolution T1 images as input.

50 min sequence (estimated 49 min 30 s)

Sequence	Approx. run time in minutes
T1-weighted MPRAGE	6:11
T2-weighted image	6:42
T2-weighted FLAIR	6:10
High Res Hippo	5:36
Diffusion MRI	8:05
Perfusion MRI	5:32
MR Spectroscopy	2:54
Functional MRI	8:20

-Optional CSF Collection Sub-Study

Lumbar Puncture (LP) is a standard neurodiagnostic procedure for collection of CSF but may be associated with pain during the performance of the procedure. This is usually temporary and confined to the lower back. A persistent low-pressure headache may develop after LP, due to leakage of CSF. Although the frequencies of post-LP headaches have been reported to be as high as 10% using standard 20 gauge spinal needles, rates of less than 2% have been reported in elderly subjects when atraumatic (Sprotte) needles are used³⁵. If a post-LP headache persists, it may need additional treatment, e.g. with fluids and analgesics. Uncommonly, a blood patch (injection of some of the subject's blood to patch the CSF leak) may be needed. Potential but rare risks of lumbar puncture include infection, damage to nerves in the back, bleeding into the CSF space, and death. The risk of these is less than 1%.

- Optional Saliva Collection Sub-Study

Saliva samples will be collected via passive drooling into plastic tubes, thus involving no risk to study subjects.

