Immuno-modulation is mostly achieved by preventing egression of lymphocytes from lymphoid organs, and the modulation of cytokine expression, including microglia⁵. For T lymphocytes, it was shown that S1PR modulators prevent the infiltration of CD8+ memory cells in the central nervous system (CNS). This property could be key for AD since, very recently, the group of Wyss-Coray showed that CD8+ T cells likely play a critical role in the adaptive immune response in the CNS of AD patients^{17,42}. On the other hand, the molecular mechanisms for neuroprotection are currently poorly understood. Nonetheless, both fingolimod and Siponimod lower the rate of brain atrophy in remitting relapsing MS (RRMS)⁷. Very interestingly, Siponimod was found to reduce brain atrophy at later stages of MS called secondary progressive MS (SPMS), making it the first drug with a demonstrated neuroprotective effect in SPMS¹². More precisely, at month 12 the percentage of total brain volume change from baseline adjusted mean were -0.28% and -0.46% ($p < 0.0001$) in Siponimod vs placebo-treated SPMS subjects, respectively²⁵.

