4. OBJECTIVES AND ENDPOINTS

OBJECTIVES	ENDPOINTS
PRIMARY	
The primary objective of the study is to assess the safety and tolerability of Siponimod in mild AD dementia subjects.	Safety will be assessed at each study visit through completion of comprehensive tests and procedures aimed at monitoring for potential adverse events (AEs). Study staff will also gather direct reports from subjects regarding any adverse events.
SECONDARY	
The secondary objective of the study is to assess the effects of Siponimod on AD-associated neurodegeneration by deriving annual brain atrophy rates from volumetric MRI (vMRI).	Siponimod was observed to slow rates of brain atrophy in both RRMS and SPMS patients. Thus, the aim is to assess the medical benefits of the drug in mild AD dementia subjects by assessing whether brain atrophy slows with Siponimod treatment. Subjects will undergo volumetric MRI (vMRI) measurements of the hippocampus, cortical thickness, and global thickness as indicators of neurodegeneration.
TERTIARY	
The tertiary objective of study is to assess the effects of Siponimod on cognition following administration of study drug vs. placebo.	Cognition will be assessed by comparing the changes in two assessments: ADCS-ADL and ADCOMS from baseline to various visit timepoints, including Week 78 (End of Study).
EXPLORATORY	
Exploratory objectives will include:	
i) measurements of markers found in the CSF fluid that are known to be associated with mild AD dementia and inflammation before and after treatment	i) CSF biomarkers that will be assessed include amyloid beta 40 & 42, Tau, and Phospho-Tau.
ii) assessment of blood inflammatory markers before and after treatment	ii) Blood inflammatory markers include CRP, TNF- α , IL-1 β , IL-6, IL-8, and IL-10 (54-plex measured on the Meso Scale Discovery [MSD] ELISA platform). Plus, we will count the number of white blood cells (B and T lymphocytes, macrophages, etc) in the blood to estimate the impact of Siponimod on peripheral markers of the immune system.
iii) to assess levels of A β found in saliva samples collected before and after treatment with Siponimod vs. placebo	iii) Saliva markers that will be assessed are A β 40 and A β 2. Saliva A β levels is a recent biomarker that has been identified to study AD. Thus, we propose to explore the effects of Siponimod on A β 40 and A β 2 throughout the course of the study.

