12. STATISTICAL CONSIDERATIONS

STATISTICAL HYPOTHESES

- Primary and Exploratory Efficacy Endpoint(s):

The null hypothesis for the primary efficacy endpoint is that biomarker measures (primary endpoint: vMRI; tertiary and exploratory endpoints: CSF biomarkers, blood inflammatory markers, saliva amyloid beta levels) will be the same in Siponimod- vs. placebo-treated study subjects after 12 months (end of dosing).

The alternative hypothesis is that Siponimod will improve biomarker measures at the same time point.

- Secondary Efficacy Endpoint(s):

The null hypothesis for the secondary efficacy endpoint is that cognitive measures (ADCOMS) will be the same in Siponimod - vs. placebo-treated study subjects after 12 (end of dosing) and 18 months (6 months follow up).

The alternative hypothesis is that Siponimod will improve cognitive measures at the same time points.

SAMPLE SIZE DETERMINATION

Mild AD subjects will receive an escalating dose of Siponimod up to 1 mg/day (N=70) or placebo (N=35) for 12 months (Table 2). We conducted a power analysis for sample size determination using the reported data from brain volume changes in SPMS subjects treated for at least 12 months with Siponimod or placebo²⁵. We wished to fit a repeated measures ANOVA model with two treatment levels in drug vs. placebo, and 4-time measures to receiving the drug (i.e. vMRI at baseline, 6, 12, and 18 months). We defined $Y_{ij} = \mu + \alpha_i + \tau_j + (\alpha\tau)_{ij} + \varepsilon_{ijk}$, where Y_{ijk} denotes the measure on brain atrophy, α_i denotes the treatment effect $i = 1, 2$; τ_j denotes the time effect at time $j=1, 2, 3, 4$; $k = 1, n$; $(\alpha\tau)_{ij}$ is the interaction between time and treatment; and ε_{ijk} is the error term²¹. We study the effect of the drug on brain atrophy. The between-subject factor in our model is treatment, with two levels (study drug and placebo), and we allocate each treatment in the ratio 2:1. The within-subject factor is time, with four levels (0, 6, 12, and 18 months). The number of patients needed is determined to achieve a power of 0.90 at significance level $\alpha = 0.05$ for the test of the interaction between time and treatment, where the contrast over time contains all pairwise comparisons. We also intend to generate a plot of power versus sample size that covers the power range of 0.05 to 0.90.

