The data will be summarized using professional standards. The distributions of patients completing each study visit and the reason for early terminations will be tabulated for each treatment group. The duration of double-blind treatment within each treatment group and compliance rates will be summarized by descriptive statistics (mean, standard error, standard deviation, median, minimum, maximum and sample size) for days of treatment and for total days of exposure and by the distributions of patients exposed to various durations of treatment categories. Demographic and baseline characteristics will be summarized by descriptive statistics for all patients in each treatment group.

Volumetric MRI data measures will be computed to determine eventual brain volume changes between pre- and post-treatment, which will validate or refute our central hypothesis. Data from Aims 2-3 will also be used in correlational analyses for blood vs. AD central markers to investigate whether minimally invasive tests that use peripheral markers could be used as proxies to track drug performance. We wish to fit a repeated measures ANOVA model with two treatment levels (drug and placebo) and 13 time measures (for blood markers). We define $Y_{ij} = \mu + \alpha_i + \tau_j + \varepsilon_{ijk}$, where Y_{ij} denotes the measure on siponimod, α_i denotes the treatment effect $i=1,2$, τ_j denotes the random effect at subject $j=1, 2, \dots, 70$, $k=1, \dots, 13$ and ε_{ijk} is the error term. We assume that the random effect is distributed with mean zero and σ^2 . Paired data tests will be used to assess eventual biomarker changes between pre- and post-dosing datasets. Correlational statistics and linear regressions will be employed to determine possible dose-response for siponimod on the biomarkers investigated. If siponimod has an effect on inflammatory and AD biomarkers (either in blood, or in CSF), the current study should demonstrate an amelioration of these biomarker profiles. Also, we will use the results of cognitive tests to calculate the average conversion rate, continuous variables, and time to event analysis in our two groups.

Missing data will not be imputed, and all summary statistics will be reported based upon observed data. For limited analyses where formal inferential analyses are specified, rank-based methods will be used to incorporate subjects missing follow-up assessments.

ANALYSIS OF THE PRIMARY EFFICACY ENDPOINT(S)

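### The protocol does not say which vMRI quantity is the lead efficacy measure, and its 90% power cannot be attached to any of those it names

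*Protocol*

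**What the plan says.** The protocol describes its main efficacy measure in five places, and they do not agree.

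- **Section 4, secondary endpoint:** "volumetric MRI (vMRI) measurements of the hippocampus, cortical thickness, and global thickness as indicators of neurodegeneration". There are three quantities, with no order.
- **Section 10, Efficacy Assessments:** annual atrophy rates are to be obtained by "comparing volumetric MRI (vMRI) values for the hippocampal, cortical, and global thickness". This is a similar list, again unranked.
- **Section 12, Sample Size Determination:** the calculation was made "using the reported data from brain volume changes in SPMS subjects treated for at least 12 months with Siponimod or placebo". Section 2.2 gives that source's result: "at month 12 the percentage of total brain volume change from baseline adjusted mean were -0.28% and -0.46" percent, siponimod versus placebo. Section 3.1.2 repeats it.
- **Section 12, General Approach:** vMRI will be used to compute brain volume changes, "which will validate or refute our central hypothesis". No region is named.
- **Section 12, Analysis of the Primary Efficacy Endpoint(s):** the only entry is vMRI, used to estimate the annual rate of atrophy.

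The MRI methods under the screening scan in section 10 give a longer list of outputs. There, "hippocampal, ventricular and whole brain volumes will be determined by automated segmentation", and the text adds cortical thickness, hippocampal subfields, voxel-based and deformation-based morphometry, and a principal-component estimate of whole-brain atrophy. No output there is called global thickness.

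**The concern.** Section 12 frames a single null hypothesis for a primary efficacy endpoint, vMRI, at 12 months. A reader needs to know which number from the scan that hypothesis concerns, and the protocol does not say. Two things are at stake.

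1. **Power.** A sample size is justified for one quantity with one mean difference and one SD. If the lead quantity is not fixed, or the inputs are not on its scale, the 90% figure describes nothing in particular.
2. **Selective claiming.** With several unranked measures and a central hypothesis that unspecified volume changes can confirm, the measure that looks best could be put forward afterwards.

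A later analysis plan could divide alpha or set a testing order. It would be a poor place to choose the lead measure for the first time, and it cannot make a sample size argued from one quantity apply to another.

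**Working it through.** **Inputs from the protocol.** Allocation 2:1; alpha 0.05 (sidedness not stated, two-sided assumed here); power 0.90; effect a 20-30% decrease; error SD about 4-11; evaluable N of 90 (power 0.903) and 94 (power 0.906) in Table 4; about 10% attrition; total 105. The cited source gives -0.28% versus -0.46%, so the difference is 0.46 - 0.28 = 0.18 points, and 0.18/0.46 = 39% in relative terms. That is already outside the assumed 20-30%.

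**Step 1: the plan's own figures.** The attrition step reproduces: 94/(1 - 0.10) = 104.4, rounded up to 105. The 90 and 94 cannot be reproduced, because the effect and the SD have no unit and the correlation between scans is not given. The text also powers the time-by-treatment interaction, while Table 4 lists only Time and Treatment effects.

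**Step 2: do the inputs fit the cited scale?** For two means at 2:1,

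N = (3 + 1.5) × (1.960 + 1.282)² × SD²/δ² = 4.5 × 10.507 × SD²/δ².

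| δ (points) | SD | Total N, two-sided, 90% power |
|---|---|---|
| 0.18 | 4 | 23,352 |
| 0.18 | 11 | 176,586 |

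This is a single-time-point approximation. Averaging four uncorrelated scans would at best halve the SD and so divide N by four, to 23,352/4 = 5,838 at SD 4, which is still far from 90.

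For the interaction test itself I used the Hotelling-Lawley F with four times and an assumed common correlation. At N = 90, power is about 5-8% for correlations up to 0.9. It reaches at most 43%, at SD 4 and correlation 0.99.

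**Step 3: work back from the stated N.** Inverting the noncentral t for a two-group comparison, N = 90 implies a standardised effect of 0.74 and N = 94 implies 0.72.

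- At SD 4 the difference would be about 2.9 units, and at SD 11 about 8. The whole placebo loss in the cited source is 0.46 points.
- For a difference of 0.18 points the SD would have to be 0.18/0.74 = 0.24 to 0.18/0.72 = 0.25.
- For 20-30% of 0.46 (0.092 to 0.138 points) the SD would have to be about 0.13 to 0.19.

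An SD of 4-11 is therefore not on the percent total brain volume scale in any way the protocol explains. Nothing ties it to hippocampal volume or cortical thickness either.

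**Step 4: several measures.** Suppose three measures were each tested at two-sided 0.05 and any one sufficed. If independent, the familywise error is 1 - 0.95³ = 14.3%. By simulation with equal correlations it is about 13.5% at 0.3, 12.5% at 0.5, 11.0% at 0.7 and 9.8% at 0.8.

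Keeping all three as co-leads with a Bonferroni split (0.0167 each) would lower power per measure from about 90% to about 80% at the standardised effect implied in Step 3. Restoring 90% would take 117 to 121 evaluable participants, or 130 to 135 enrolled at 10% attrition.

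**The case against.** The strongest reply is that whole-brain volume is not absent. The MRI methods derive whole-brain volume and a longitudinal whole-brain atrophy estimate, the general approach speaks of brain volume changes, and other sections speak of brain atrophy. Global thickness may simply be a slip for global volume. This stands in part. A reader might infer that the powered measure is not the one tested. The documents do not show that: total brain volume may well be analysed. Nor is it certain that total brain volume is what was powered, since the effect and SD entered do not match it. What remains is that the protocol leaves both open.

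A second reply is that no sentence says each measure is tested at 0.05 or that one success is enough, and that an alpha split may sit in a SAP not at hand. This also stands. The 11-14% is conditional on that rule and is not a property of the written plan.

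A third is that efficacy is a secondary objective in a proof-of-concept trial whose primary objective is safety and tolerability. That limits the weight of the point but does not remove it, because the sample size is argued entirely from the vMRI comparison.

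A fourth is that both endpoint lists put the hippocampus first and a dedicated hippocampal sequence is acquired, so whole-brain volume may not be the intended lead. That is fair: the choice is the sponsor's, but it has to be made.

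**Conclusion.** The point holds. The protocol defines its main efficacy measure as several unranked vMRI quantities. Its sample-size source concerns a quantity that neither endpoint list names, and the effect and SD it enters have no unit and do not fit that source. The stated 90% power therefore cannot be attached to any named measure.

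The SD of 4-11 would have to be near 0.25 for a 0.18-point difference to give the stated N. This rests on the cited means, 2:1 allocation, two-sided alpha and a two-group approximation. The repeated-measures check, with an assumed common correlation up to 0.99, does not rescue the figure. The 23,000 obtained at SD 4 shows that the units do not match; a reader should not take it as the size this trial needs.

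The false-positive figure of about 11-14% applies only if three measures are each tested at 0.05 and any one suffices, with correlations between 0 and 0.7. Nothing in the protocol prevents that. The change should be made, but it does not touch the primary safety objective.

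**What to change.** 1. In section 4, in Efficacy Assessments (section 10) and in Analysis of the Primary Efficacy Endpoint(s) (section 12), name one lead vMRI measure and one time point. Percent whole-brain volume change from Baseline to Week 52 is the natural choice: it matches the cited source and the 12-month null hypothesis, and whole-brain volume is already derived from the scans.
2. Label hippocampal, cortical and voxel-wise measures supportive.
3. Define *global thickness*, or correct it if volume was meant.
4. In Sample Size Determination, restate the effect, SD and between-scan correlation on the lead measure's scale with units, state which model term is tested, and report the resulting power for the planned 105 participants (105 × 0.90 = 94.5, so about 94 evaluable). Do not carry the 90% over from the present calculation.

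The cost is protocol wording and one recalculation; no extra scans are needed. A result confined to the hippocampus would become supportive, and the restated power may be less favourable than 90%.
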